5.4 Recording of Adverse Events

AEs will be recorded on the eCRF using a recognized medical term or diagnosis that accurately reflects the event. AEs will be assessed by the investigator for severity, relationship to the investigational product, possible etiologies, and whether the event meets criteria of an SAE and therefore requires immediate notification to the sponsor (see Section 5.5). See Section 5.3 for the definition of SAEs and Section 10.2 for guidelines for assessment of severity and relationship.

If an AE evolves into a condition that meets the regulatory definition of “serious,” it will be reported on the SAE Report Form.

Infusion of biological products is commonly associated with infusion related reactions. Anaphylaxis and infusion related reactions have some common manifestations and may be difficult to distinguish from each other. Infusion related reactions are commonly observed during or shortly after the first time of exposure to therapeutic monoclonal antibodies delivered through IV infusion. These reactions are less common following subsequent exposures. Unlike infusion related reactions, anaphylaxis is a rare event, usually occurring after subsequent exposure to an antigen, and it is most commonly accompanied by severe systemic, skin and/or mucosal reactions. The investigator is advised to carefully examine symptoms of adverse reactions observed during or shortly after exposure to MEDI6012, and consider the above mentioned facts prior to making a final diagnosis. Reactions occurring at the time of or shortly after subsequent infusions of investigational product are to be judged by the investigator at his/her own discretion. For the investigator’s convenience and in order to facilitate consistency in judgments a copy of the National Institute of Allergy and Infectious Disease and Food and Allergy Anaphylaxis Network (FAAN) guidance for anaphylaxis diagnosis is provided in Section 10.4.

5.4.1 Time Period for Collection of Adverse Events

AEs will be collected from time of randomization throughout the treatment period until the end of the follow-up period(s).

All SAEs will be recorded from the time of informed consent.

Non-TEAEs (ie, AEs that occur during the period from the time informed consent is signed but prior to the subject receiving investigational product) should not be reported. However,

nontreatment SAEs associated with protocol related procedures should be reported. After the start of treatment, all TEAEs (Section 5.1) should be reported.

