4.5.1.4 Treatment Administration

The first day of dosing is considered Day 1. On Day 1, investigational product will be administered following verbal or written informed consent and should be prior to pPCI (as soon as possible prior to pPCI, defined as the time that the first angioplasty wire crosses the culprit lesion). In rare cases when investigational product is not administered prior to PCI in a subject who has already been randomized, then the first dose will be administered as soon as possible post-PCI. Subsequent doses will be administered following an overnight fast for a minimum of 6 hours, as soon as is practicable after rising. Subjects should be instructed on whether their regular medications can be taken while fasting.

Investigational product will be administered by IV push over approximately 1-2 minutes, inclusive of flush.

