4.8.3.4 Exploratory Analyses

The exploratory objectives are to determine whether MEDI6012

█

Incidence of CV death or heart failure and incidence of CV death, MI, unstable angina or urgent coronary revascularization from randomization to final study visit (10-12 weeks post-randomization) will be calculated. Time to first major adverse CV event will be analyzed using log-rank test.

The proportion of TFG at baseline (on initial angiography, pre-PCI) and the proportion of subjects with decline in renal functions at 48 hours will be compared between MEDI6012 and placebo using chi-square test.

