5.5 Reporting of Serious Adverse Events

All SAEs have to be reported, whether or not considered causally related to the investigational product, or to the study procedure(s). All SAEs will be recorded in the eCRF.

If any SAE occurs in the course of the study, then investigators or other site personnel must inform the appropriate sponsor representative(s) within 1 day, ie, immediately but no later than 24 hours after becoming aware of the event.

The designated sponsor representative works with the investigator to ensure that all the necessary information is provided to the sponsor's patient safety data entry site within 1 calendar day of initial receipt for fatal and life-threatening events and within 5 calendar days of initial receipt for all other SAEs.

For fatal or life-threatening AEs where important or relevant information is missing, active follow-up is undertaken immediately. Investigators or other site personnel inform sponsor representatives of any follow-up information on a previously reported SAE within 1 calendar day, ie, immediately but no later than 24 hours after becoming aware of the event.

Once the investigators or other site personnel indicate an AE is serious in the electronic data capture (EDC) system, an automated email alert is sent to inform the designated sponsor representative(s).

If the EDC system is not available, then the investigator or other study site personnel reports an SAE to the appropriate sponsor representative by telephone. The sponsor representative will advise the investigator/study site personnel how to proceed. The AE/SAE should be reported in the EDC as soon as it becomes available.

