- Laboratory tests. A specific laboratory investigation (if performed) has confirmed the relationship?

In difficult cases, other factors could be considered such as:

- Is this a recognized feature of overdose of the investigational product?
- Is there a known mechanism?

Causality of ‘related’ is made if following a review of the relevant data, there is evidence for a ‘reasonable possibility’ of a causal relationship for the individual case. The expression ‘reasonable possibility’ of a causal relationship is meant to convey, in general, that there are facts (evidence) or arguments to suggest a causal relationship.

The causality assessment is performed based on the available data including enough information to make an informed judgment. With limited or insufficient information in the case, it is likely that the event(s) will be assessed as ‘not related’.

Causal relationship in cases where the disease under study has deteriorated due to lack of effect should be classified as no reasonable possibility.

Relationship to Protocol Procedures

The investigator is also required to provide an assessment of relationship of SAEs to protocol procedures on the SAE Report Form. This includes nontreatment-emergent SAEs (ie, SAEs that occur prior to the administration of investigational product) as well as treatment-emergent SAEs. A protocol-related SAE may occur as a result of a procedure or intervention required during the study (eg, blood collection, washout of an existing medication). The following guidelines should be used by investigators to assess the relationship of SAEs to the protocol:

Protocol related: The event occurred due to a procedure/intervention that was described in the protocol for which there is no alternative etiology present in the subject’s medical record.

Not protocol related: The event is related to an etiology other than the procedure/intervention that was described in the protocol (the alternative etiology must be documented in the study subject’s medical record).

10.4 Appendix 4 - National Institute of Allergy and Infectious Disease and Food Allergy and Anaphylaxis Network Guidance for Anaphylaxis Diagnosis

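### Section 5.4.1 contradicts itself and Section 5.5 on whether events before the first dose are reported, so some serious events in randomized, undosed subjects could be omitted

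*Protocol*

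**What the plan says.** Protocol 5.4.1 has three parts. The first sets the AE start: "AEs will be collected from time of randomization throughout the treatment period until the end of the follow-up period(s". The second says that all SAEs are recorded from informed consent. The third turns to events before treatment: those occurring after consent is "signed but prior to the subject receiving investigational product) should not be reported". It then makes one exception, that "nontreatment SAEs associated with protocol related procedures should be reported".

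Other sections bear on the same events:

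- Protocol 5.2 defines a non-treatment-emergent AE as any untoward event that begins after consent and before product is received. The definition is not limited to non-serious events.
- Protocol 5.5 states: "All SAEs have to be reported, whether or not considered causally related to the investigational product, or to the study procedure(s"). It also requires all SAEs to be entered in the eCRF.
- Appendix 3 asks the investigator to judge whether SAEs are related to protocol procedures and adds: "This includes nontreatment-emergent SAEs (ie, SAEs that occur prior to the administration of investigational product) as well as treatment-emergent SAEs".
- Footnote i of Tables 8 and 9, Protocol 4.8.4.1 and SAP 3.6.1 all start AEs at randomization and SAEs at consent. The synopsis starts AEs at consent.
- Protocol 4.5.1.4 provides for rare cases in which a randomized subject is not dosed before PCI: "then the first dose will be administered as soon as possible post-PCI". Protocol 4.1.7 provides for subjects who never receive product, with one end-of-study phone call as the minimum follow-up. SAP 3.3.1 plans a summary of subjects randomized but not treated.
- Protocol 4.8.3.4 says the incidence of the CV composites "from randomization to final study visit (10-12 weeks post-randomization) will be calculated".

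**The concern.** The section that sets the collection period gives two answers for the same event. For a subject who is never dosed, the period before receipt of product has no end, so on a literal reading every later event falls under the instruction not to report. For a subject dosed only after PCI, the instruction covers the interval from randomization through the procedure.

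These people are randomized and belong to the ITT population. Whether they are dosed is settled after randomization, and an early serious event may itself be why the dose was not given. If their events are not entered, the loss depends on a post-randomization variable, and the CV outcomes counted from randomization could be incomplete. Before declaring futility, the IDMC also weighs CV death, heart failure, MI and stroke (SAP Section 4). Safety review depends on entry too: the safety desk and medical monitor are notified when an SAE is entered (Protocol 5.1, 5.5).

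**Working it through.** No arithmetic applies. The documents give no count of undosed subjects, no interval from randomization to dose, and no CV event rate. The check is a comparison of the rules by type of event.

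| Event | 5.4.1, first two parts | 5.4.1, third paragraph | 5.5 and Appendix 3 |
|---|---|---|---|
| Non-serious AE, consent to randomization | Not collected (synopsis: collected) | Not reported | Silent |
| Non-serious AE, randomization to first dose | Collected | Not reported | Silent |
| Pre-dose SAE associated with a protocol procedure | Recorded | Reported | Reported |
| Pre-dose SAE not associated with a protocol procedure | Recorded | Not reported | Reported |

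1. The second row is a contradiction inside 5.4.1. The fourth row is a contradiction between the third paragraph and both the second part of 5.4.1 and Section 5.5.
2. Could the third paragraph apply only to non-serious AEs? The definition in 5.2 has no such limit. The exception for procedure-associated SAEs is needed only if SAEs fall under the instruction in the first place.
3. Could recording be one duty and reporting another? The protocol does not draw that line. Section 5.5 requires both for every SAE and speaks of reporting events in the EDC.
4. Appendix 3 asks whether a pre-dose SAE is procedure-related. If only the related ones are submitted, the question has one possible answer.
5. Which analyses could be touched? The As-treated Population requires receipt of product (Protocol 4.8.1.1, SAP Table 3.1), so never-dosed subjects are outside the safety tables under any reading. For dosed subjects, pre-dose events are not treatment-emergent and do not belong in the TEAE tables. The primary endpoint is a CMR measurement and does not depend on AE reporting. That leaves the CV outcomes counted from randomization and the safety review of individual events.
6. The third paragraph also cites Section 5.1 for TEAEs, which are defined in 5.2. This suggests that the paragraph was not reconciled with its neighbours.

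**The case against.** The strongest reply is that the SAE rule is clear almost everywhere else. Tables 8 and 9, Protocol 4.8.4.1, Protocol 5.5 and SAP 3.6.1 all point to SAEs from consent, and a serious event goes missing only if a site follows one paragraph against all of these. That stands as a limit on the consequence. It does not remove the conflict, because no order of precedence is stated and 5.4.1 is where a site looks for the collection period.

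A second reply is that CV events have their own route. Protocol 4.1.7 sends possible events to the CEC, and SAP Section 4 uses adjudicated and unadjudicated events. This also stands in part. The CEC text is written for follow-up after product is discontinued, and it acts only once an event is noted. The visible text does not say what data source or population the CV composites use. Some of the exploratory text is redacted, so this cannot be checked and is not a fault in the plan.

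Three stronger readings are tempting, and the documents do not support them:

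- A reader might infer that the treatment comparison is biased. An event before any dose cannot be caused by the product, and nothing in the documents shows that omission would differ by arm.
- A reader might put a number on the lost events. Every rate needed would have to be assumed, and one rate could not serve both never-dosed subjects, at risk for the whole follow-up, and late-dosed subjects, who by definition survived to be dosed.
- A reader might infer that every PCI complication before a late dose goes unreported because PCI is standard care. The text does not settle this. Appendix 3 ties relatedness to procedures described in the protocol and requires that the record show no alternative cause. Planned pPCI is an inclusion criterion, so sites could classify such an event either way.

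**Conclusion.** The contradiction is real and stands whatever the number of events. As written, a site may properly conclude that an SAE before dosing, or in a never-dosed subject, need not be reported unless it is procedure-associated, while another site following 5.5 reports it. Loss of such events, including deaths, is possible but not certain, and its size cannot be estimated from the documents. The outcomes exposed are exploratory, and the exposure assumes that the CV composites include all randomized subjects and draw at least partly on site-reported events, which the visible text neither confirms nor excludes. In dosed subjects the exposed window is normally short, because Dose 1 is planned before pPCI; most of the exposure lies with never-dosed subjects. Severity: minor.

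**What to change.** Replace the third paragraph of Protocol 5.4.1 with a single rule: all SAEs from first consent are recorded and reported, whatever their relation to study procedures and whether or not product is given; AEs are recorded from randomization; events before the first dose are flagged as non-treatment-emergent and kept out of the TEAE and TESAE tables. Correct the cross-reference for TEAEs to 5.2, and align the AE start in the synopsis with 5.4.1, 4.8.4.1 and SAP 3.6.1.

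In SAP 3.6, add a listing by randomized arm of deaths and SAEs in randomized subjects that occur before dosing or without dosing. Without it, events in never-dosed subjects would be collected but would appear in no safety output, since those outputs use the As-treated Population.

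The cost is one paragraph of protocol text, a synopsis edit, one listing, and a few more recorded events. The TEAE summaries do not change.

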5.4.2 Follow-up of Unresolved Adverse Events

Any AEs that are unresolved at the subject's last visit in the study are followed up by the investigator for as long as medically indicated, but without further recording in the eCRF. MedImmune retains the right to request additional information for any subject with ongoing AE(s)/SAE(s) at the end of the study, if judged necessary.

5.5 Reporting of Serious Adverse Events

All SAEs have to be reported, whether or not considered causally related to the investigational product, or to the study procedure(s). All SAEs will be recorded in the eCRF.

If any SAE occurs in the course of the study, then investigators or other site personnel must inform the appropriate sponsor representative(s) within 1 day, ie, immediately but no later than 24 hours after becoming aware of the event.

The designated sponsor representative works with the investigator to ensure that all the necessary information is provided to the sponsor's patient safety data entry site within 1 calendar day of initial receipt for fatal and life-threatening events and within 5 calendar days of initial receipt for all other SAEs.

For fatal or life-threatening AEs where important or relevant information is missing, active follow-up is undertaken immediately. Investigators or other site personnel inform sponsor representatives of any follow-up information on a previously reported SAE within 1 calendar day, ie, immediately but no later than 24 hours after becoming aware of the event.

Once the investigators or other site personnel indicate an AE is serious in the electronic data capture (EDC) system, an automated email alert is sent to inform the designated sponsor representative(s).

If the EDC system is not available, then the investigator or other study site personnel reports an SAE to the appropriate sponsor representative by telephone. The sponsor representative will advise the investigator/study site personnel how to proceed. The AE/SAE should be reported in the EDC as soon as it becomes available.

5.6 Other Events Requiring Immediate Reporting

5.6.1 Overdose

An overdose is defined as a subject receiving a dose of investigational product in excess of that specified in this protocol.

- An overdose with associated AEs is recorded as the AE diagnosis/symptoms on the relevant AE modules in the eCRF and on the Overdose eCRF module.
- An overdose without associated symptoms is only reported on the Overdose eCRF module.

If an overdose on a MedImmune investigational product occurs during the course of the study, then the investigator or other site personnel inform appropriate sponsor representatives immediately, or no later than 24 hours after becoming aware of the event.

The designated sponsor representative works with the investigator to ensure that all relevant information is provided to the sponsor's Patient Safety data entry site.

For overdoses associated with an SAE, the standard reporting timelines apply; see Section [5.5](#). For other overdoses, reporting must occur within 30 days.

5.6.2 Hepatic Function Abnormality

Patients with acute STEMI are very likely to show aminotransferase elevations at inclusion, either originating from cardiomyocytes, or, if released from hepatocytes, related to hepatic ischemia or congestion. Definition of potential signals for Drug-Induced Liver Injury and requirements for expedited reporting need to be adapted accordingly. Please refer to Section [10.5](#) for details.

5.6.3 Pregnancy

All pregnancies and outcomes of pregnancy should be reported to the Sponsor.

5.6.3.1 Maternal Exposure

Women of childbearing potential are not allowed to be included in this study.

5.6.3.2 Paternal Exposure

Nonsterilized male study subjects who are sexually active with a female partner of childbearing potential must use condom and spermicide from Day 1 through the end of the study follow-up period.

Male subjects should refrain from fathering a child or donating sperm during the study and for 12 weeks following the last dose.

Pregnancy of the subject's partner is not considered to be an AE. However, the outcome of all pregnancies (spontaneous miscarriage, elective termination, ectopic pregnancy, normal birth, or congenital abnormality) should if possible be followed up and documented.

The outcome of any conception occurring from the date of the first investigational product administration until 12 weeks after the last investigational product administration should be

followed up and documented. Information on the pregnancy of a subject's partner must be obtained directly from the subject's partner. Therefore, prior to obtaining information about the pregnancy, the Investigator must obtain the consent of the subject's partner.

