3.1.2 Treatment Regimen

Enrolment of approximately 540 subjects is planned to evaluate the █ dosing regimens (Cohort A: █ regimen and Cohort B: █ regimen) as follows:

Cohort A

- MEDI6012, █ (n ~ 180)
- Placebo, █ (n ~ 90)

Cohort B

- MEDI6012, █ (n ~ 180)
- Placebo, █ (n ~ 90)

Inpatient Phase Dosing

Both Cohort A and Cohort B inpatient dosing will consist of a [REDACTED] loading dose of Investigational Product administered on Day 1, followed on Day 3 by a [REDACTED] second dose, both administered in the inpatient setting ([Table 6](#) and [Table 7](#)). Dosing for Cohort A will be completed at this point.

Table 6 Dosing for Cohort A: [REDACTED] Regimen

Day	Dose	Route	Time
1	[REDACTED]	[REDACTED]	[REDACTED]
3	[REDACTED]	[REDACTED]	[REDACTED]
10, 17, 24, 31	[REDACTED]	[REDACTED]	[REDACTED]
10, 17, 24, 31	[REDACTED]	[REDACTED]	[REDACTED]

For Cohort B, additional maintenance doses of [REDACTED] mg will be administered at weekly intervals on Days 10, 17, 24, and 31 ([Table 7](#)). These doses will be administered in the outpatient setting.

Table 7 Dosing for Cohort B: [REDACTED] Regimen

Day	Dose	Route	Time
1	[REDACTED]	[REDACTED]	[REDACTED]
3	[REDACTED]	[REDACTED]	[REDACTED]
10, 17, 24, 31	[REDACTED]	[REDACTED]	[REDACTED]
10, 17, 24, 31	[REDACTED]	[REDACTED]	[REDACTED]

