10.2 Appendix 2 – Contraception Guidance

For females:

Females without childbearing potential will be included in this study. Females without childbearing potential are defined as those who are surgically sterile (ie, surgical sterilization includes bilateral tubal ligation, bilateral oophorectomy, or hysterectomy) or those who are postmenopausal (defined as 12 months with no menses without an alternative medical cause).

For males:

Nonsterilized males who are sexually active with a female partner of childbearing potential must use condom and spermicide from Day 1 through the end of their participation in the study. Because male condom and spermicide is not a highly effective contraception method it is strongly recommended that female partners of a male study subjects also use a highly effective method of contraception throughout this period. A highly effective method of contraception is defined as one that results in a low failure rate (ie, less than 1% per year) when used consistently and correctly. The acceptable methods of contraception are described in [Table 13](#).

Table 13 Highly Effective Methods of Contraception

Barrier Methods	Hormonal Methods

 • Intrauterine device • Intrauterine hormone-releasing system (UIS)^a • Bilateral tubal occlusion • Vasectomized partner^b • Sexual abstinence^c 	
Combined (estrogen and progestogen containing hormonal contraception)
 
 ◦ Oral (combined pill) ◦ Injectable ◦ Transdermal (patch) 
Progestogen-only hormonal contraception associated with inhibition of ovulation^d
 
 ◦ Injectable ◦ Implantable ◦ Intravaginal

^a This is also considered a hormonal method.

^b With appropriate post-vasectomy documentation of surgical success (absence of sperm in ejaculate).

^c Sexual abstinence is considered a highly effective method only if defined as refraining from heterosexual intercourse during the entire period of the study and if it is the preferred and usual lifestyle of the subject.

^d Progestogen-only hormonal contraception, where inhibition of ovulation is not the primary mode of action (eg, minipill), is not accepted as a highly effective method.

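### For men, the required contraceptive method ends at the close of follow-up (Visit 6 for most), up to about six weeks before the protocol's own 12-week post-dose window ends

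*Protocol*

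**What the plan says.** The Protocol sets two end points for the same paternal exposure.

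- **Method.** Section 5.6.3.2 says that men who are not sterilized and are sexually active with a partner who could become pregnant "must use condom and spermicide from Day 1 through the end of the study follow-up period". Appendix 2 (Section 10.2) repeats this: they "must use condom and spermicide from Day 1 through the end of their participation in the study". Because condom with spermicide is not counted as highly effective, Appendix 2 adds that "it is strongly recommended that female partners of a male study subjects also use a highly effective method of contraception throughout this period". The partner method therefore runs for the same period as the condom rule.
- **Conception and its capture.** Section 5.6.3.2 continues: "Male subjects should refrain from fathering a child or donating sperm during the study and for 12 weeks following the last dose". Sites are also to follow up and record this: "The outcome of any conception occurring from the date of the first investigational product administration until 12 weeks after the last investigational product administration".
- **Reporting.** Section 5.6.3 says: "All pregnancies and outcomes of pregnancy should be reported to the Sponsor". Section 5.6.3.2 says: "Pregnancy of the subject's partner is not considered to be an AE".
- **Dosing.** Cohort A finishes on Day 3. In Cohort B (Section 3.1.2) the maintenance doses "will be administered at weekly intervals on Days 10, 17, 24, and 31".
- **Last visit.** Section 4.3.1 names Day 70-84 as the final study visit, and Tables 8 and 9 label it as follow-up.

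**The concern.** The sponsor treats the 12 weeks after the last dose as a time when conception should be avoided and tracked. The instruction that names a method to achieve this stops earlier for most men, and the recommended partner method stops with it. A man who follows the text as written could end both at Visit 6 while still being asked not to father a child.

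Capture also weakens in the gap. The duty to report pregnancies still stands, but no routine contact is scheduled, so reporting depends on the man coming forward. A partner's pregnancy is not an adverse event, and Tables 8 and 9, as far as they can be read in the available copy, list no check for one. Adverse event questioning at Visit 6 or at a COVID-delayed visit would not by itself find it.

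Section 4.2.1.1 sends all remaining subjects to Cohort B, where a full course gives the longest gap. What is at stake is a safety instruction given to participants. No trial result depends on it.

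**Working it through.** The Protocol gives no study day for the end of the 12-week window, so there is no stated figure to reproduce. The check is day arithmetic.

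**Inputs**
- Window after the last dose: 12 weeks = 12 × 7 = 84 days (Section 5.6.3.2).
- Possible last-dose days: 1 and 3 (both cohorts); 10, 17, 24 and 31 (Cohort B) (Section 3.1.2). Under Section 4.1.7, subjects who stop dosing early stay in follow-up, so each row below can occur.
- End of the required method for most men: Visit 6, Day 70 to Day 84.

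**Formulas**
- End of window = last-dose day + 84.
- Shortest gap = end of window − 84 (latest Visit 6).
- Longest gap = end of window − 70 (earliest Visit 6).

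| Last dose | End of 12 weeks | Gap after Visit 6 (days) |
|---|---|---|
| Day 1 | Day 85 | 1 to 15 |
| Day 3 (full course, Cohort A) | Day 87 | 3 to 17 |
| Day 10 | Day 94 | 10 to 24 |
| Day 17 | Day 101 | 17 to 31 |
| Day 24 | Day 108 | 24 to 38 |
| Day 31 (full course, Cohort B) | Day 115 | 31 to 45 |

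**Sensitivity to day counting**
- The ±1 day dosing window moves the Cohort B end date to Day 114-116.
- If Visit 6 is read as 70-84 days after Dose 1, it falls on Day 71-85. Each gap then shortens by one day: 115 − 85 = 30 to 115 − 71 = 44 for a Day 31 dose, and 87 − 85 = 2 to 87 − 71 = 16 for a Day 3 dose.

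**Men whose participation lasts longer**
- Extended Follow-up (Section 4.2.2): the first visit is at Week 25, Day 175, or Day 161 at the early end of its two-week window. Both fall after Day 115, so there is no gap.
- Repeat CMR (Section 4.3.8): at its latest, about Day 112, it leaves 115 − 112 = about 3 days after a full Cohort B course.
- COVID-delayed blood visit (Section 4.2.1.1): allowed up to 150 days after Dose 1. It closes the gap only if it falls on or after the man's 12-week date.

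No section of the Protocol carries the method itself to 12 weeks after the last dose.

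**The case against.** The strongest reply is that no day is left without an instruction: the request not to father a child or donate sperm covers the whole 12 weeks. A mandatory method during participation, followed by a general instruction afterwards, need not be a contradiction. It is true that the window is covered by that request. But it states an aim and drops the means, just after Appendix 2 has judged condom and spermicide weak enough to advise adding a partner method.

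A second reply concerns exposure. The Amendment 4 summary (Section 9.3) explains that certain late PK samples, including the Cohort B sample at Day 70-84, need not all be assayed because drug is expected to be below quantification. That suggests the later weeks are a margin. It is a reason for not assaying samples, however, and it does not revise the 12-week window that Section 5.6.3.2 still sets.

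Several limits stand:
- The method rule concerns only men who are not sterilized and have a partner who could conceive, in a population aged 30-80. The documents give no count of them.
- One third of subjects under 2:1 randomization, and half under 1:1, receive placebo. Subjects are blinded, though, and the instruction makes no distinction by arm.
- For a last dose on Day 1 or Day 3 the gap can be only a few days.
- Reliance on the man's own report is not peculiar to the gap, and a longer method rule would not cure it.
- The consent form was not available. It may already say more than the Protocol does.

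**Conclusion.** The concern holds. Section 5.6.3.2 and Appendix 2 end the required method, and the recommended partner method, before the 12-week window that Section 5.6.3.2 itself sets. The shortfall is 31 to 45 days for a man who completes dosing in Cohort B and 3 to 17 days for a man whose last dose is on Day 3, give or take about a day.

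This assumes that follow-up and participation end at Visit 6, as they do unless Extended Follow-up, a repeat CMR or a COVID-delayed visit applies. It rests on the Protocol text alone. The documents do not show how much reproductive risk remains in the gap, and none is asserted. The point does not bear on efficacy. It should be corrected because it is a participant safety instruction that lapses early if followed as written.

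**What to change.** In Section 5.6.3.2 and Appendix 2, state that condom and spermicide, and the recommended partner method, continue until the end of the study or 12 weeks after the last dose, whichever is later. The words on the later date keep the present requirement intact for men in Extended Follow-up. Check the consent form and align it if needed.

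At Visit 6, tell each man concerned his own end date (last dose + 84 days) and remind him to report any partner pregnancy conceived before it.

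The cost is a wording change in two Protocol sections and, where needed, the consent form, plus a one-line reminder at a visit that already exists. No new visit or telephone call is required.
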